5.1.2 AE date imputation

AE date imputation need to be done twice, once for Week 24 analysis, and once for the End of study analysis.

AE end date imputation

1. If ‘month’ is missing, the end date will be set to the earliest of the (min (last visit date, last dose date), 31DECYYYY, and date of death).
2. If ‘day’ is missing, the end date will be set to the earliest of the (min (last visit date, last dose date), 31MONYYYY, and date of death).
3. If ‘year’ is missing or AE is ongoing, the end date will not be imputed.

AE start date imputation

Before imputing AE start date, find the AE start reference date.

- If the (imputed) AE end date is complete and the (imputed) AE end date < treatment start date then AE start reference date = min (informed consent date, earliest visit date).
- Else AE start reference date = treatment start date

After finding the AE start reference date:

1. If ‘year’ is missing, the date uncertainty is too high; therefore the imputed AE start date will be set to NULL.
2. If ‘year’ is less than the treatment start date ‘year’, the AE started before treatment; therefore:
 - a. If ‘month’ is missing, the AE start date will be set to 01JULYYYY.
 - b. If ‘day’ is missing, the AE start date will be set to 15 MONYYYY.
3. If ‘year’ is greater than the treatment start date ‘year’, the AE started after treatment; therefore:
 - a. If ‘month’ is missing, the AE start date will be set to 01JANYYYY.
 - b. IF ‘month’ is not missing, the AE start date will be set to the later of (01MONYYYY, AE start reference date + 1).

4. If 'year' is equal to the treatment start date 'year'
 - a. If 'month' is missing, the AE start date will be set to the AE reference start date +1.
 - b. If 'month' is less than the treatment start 'month', the AE start date will be set to 15MONYYYY.
 - c. If 'month' is equal to or greater than the treatment start 'month', the AE start date will be set to the later of (01MONYYYY, AE start reference date+1).

If complete (imputed) AE end date is available and the imputed AE start date is greater than the (imputed) AE end date, imputed AE start date will be set to the (imputed) AE end date.

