2.1.1 General definitions

Baseline (Week 0) for Week 24 analysis and overall analysis including both Epoch 3 and Epoch 4 data will be defined as the last measurement before or at the randomization visit. Baseline for End of study analysis including Epoch 4 data only will be defined as the last measurement in Epoch 3.

The first day of administration of randomized study treatment (first dose) is defined as Day 1 for the study. If the date of first administration is missing, then randomization date will be used as Day 1.

All other study days will be labeled relative to Day 1. For event dates on or after Day 1, study day for a particular event date is calculated as [Date of event] – [Date of first dose] + 1. For the dates before Day 1, study day for an event date is calculated as [Date of event] – [Date of first dose]. Duration of an event will be calculated as [Event end date] – [Event start date] + 1. The descriptor “Day 0” will not be used.

For Week 24 analysis, the treatment groups presented are:

- LIK066 2.5 mg qd
- LIK066 10 mg qd
- LIK066 50 mg qd
- LIK066 150 mg qd
- LIK066 2.5 mg bid
- LIK066 5 mg bid
- LIK066 25 mg bid
- LIK066 50 mg bid
- Placebo
- Total (if applicable)

For End of study analysis, unless specified otherwise, the following treatment grouping strategy will be used, expressed as per the Epoch 3 treatment/Epoch 4 treatments a subject is assigned to at randomization:

- LIK066 qd any dose/LIK066 25 mg qd, shortened as LIK066 qd/LIK066 25 mg qd
- LIK066 bid any dose/LIK066 35 mg qd, shortened as LIK066 bid/LIK066 35 mg qd
- Placebo/LIK066 25 mg qd
- Placebo/placebo, shortened as Placebo
- Total (if applicable)

For End of study AE listings, the 10 randomized treatments will be used, as shown in Section 1.1 study design, along with the additional two pooled groups:

- LIK066 qd any dose/LIK066 25 mg qd, shortened as LIK066 qd/LIK066 25 mg qd
- LIK066 bid any dose/LIK066 35 mg qd, shortened as LIK066 bid/LIK066 35 mg qd
- Total (if applicable)

For overall analysis including both Epoch 3 and Epoch 4 treatment, the 10 randomized treatment grouping strategy will be used, as shown in Section 1.1 Study design.

For the Week 24 analyses, data collected up to the end date of Epoch 3 will be included. For AEs and concomitant medications, this means that events with start dates prior to the end of Epoch 3 dates are included.

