Week 24 on-treatment AEs are defined as any treatment-emergent AEs occurred while patients were on Epoch 3 treatment (captured using treatment start and end date). On-treatment AEs, serious AEs, fatal AEs, AEs leading to study drug discontinuation, and AEs of special interest will also be summarized.

End of study analysis

A treatment-emergent AE for the End of study analysis is defined as any AE that develops after the start of Epoch 4 or any event already present in Epoch 3 that worsens following exposure to the study treatment during Epoch 4. AEs occurring after treatment discontinuation will also be considered as treatment-emergent AEs. The number and percentage of subjects having AEs, SAEs, AEs leading to study medication permanent discontinuation and study drug interruption occurring after start of Epoch 4 will be summarized and presented, in similar way as for the Week 24 analysis.

Overall treatment emergent AEs for the overall 48 weeks of Epoch 3 plus Epoch 4 by 10 randomized treatments will be generated.

All AEs in the database will be listed by 10 randomized arms. The listings will include those AEs reported during the run-in epoch, and AEs reported after study completion or discontinuation.

Legal requirement for AE reporting

For the legal requirements of ClinicalTrials.gov and EudraCT, two required tables on treatment emergent AEs which are not SAEs with an incidence greater than 2% and on treatment emergent SAEs and SAEs suspected to be related to study treatment will be provided by system organ class, preferred term, and 10 randomized treatment arms on the SAF for overall study duration.

If for a same patient, several consecutive AEs (irrespective of study treatment causality, seriousness and severity) occurred with the same SOC and PT:

- a single occurrence will be counted if there is ≤ 1 day gap between the end date of the preceding AE and the start date of the consecutive AE
- more than one occurrence will be counted if there is > 1 day gap between the end date of the preceding AE and the start date of the consecutive AE

For occurrence, the presence of at least one SAE/SAE suspected to be related to study treatment/non SAE has to be checked in a block e.g., among AE's in a ≤ 1 day gap block, if at least one SAE is occurring, then one occurrence is calculated for that SAE.

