5.1 Imputation rules

5.1.1 Study drug

Any partial dates will be imputed as the earlier day of

- The last day in the month and
- The end day of the corresponding epoch

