5.1.3 Concomitant medication date imputation

CM date imputation need to be done twice, once for Week 24 analysis and once for the End of study analysis.

CM end date imputation

1. If 'day' is missing and 'month/year' are non-missing then impute date as the earlier of (treatment end date, and 31MONYYYY).
2. If 'day/month' are missing and 'year' is non-missing then impute date as the earlier of (treatment end date, and 31DECYYYY).
3. If imputed end date is less than the start date, use the start date as the imputed end date.

CM start date imputation

1. If 'year' is missing, the start date will be set to one day prior to treatment start date.
2. If 'year' is less than treatment start 'year', the CM started before treatment. Therefore:
 - a. If 'month' is missing, the start date will be set to 01JULYYYY.
 - b. If 'month' is non-missing, the start date will be set to 15MONYYYY.
3. If 'year' is greater than treatment start 'year', the CM started after treatment. Therefore:
 - a. If 'month' is missing, the start date will be set to 01JANYYYY.
 - b. If 'month' is non-missing, the start date will be set to 01MONYYYY.
4. If 'year' is equal to the treatment start date 'year'
 - a. If 'month' is missing or equal to the treatment start 'month', then the start date will be set to one day prior treatment start date.
 - b. If 'month' is less than the treatment start 'month', the start date will be set to 15MONYYYY.
 - c. If 'month' is greater than the treatment start 'month', the start date will be set to 01MONYYYY.

If complete (imputed) CM end date is available and the imputed CM start date is greater than the (imputed) CM end date, then imputed CM start date will be set to the (imputed) end date.

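### SAP 5.1.2 caps a partial AE end date at the last dose even when the AE began after it, which creates false on-treatment events or end dates before the start

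*SAP*

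**What the plan says.** SAP 5.1.2 gives the rules for partial adverse event (AE) dates.

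- **End, day missing:** "the end date will be set to the earliest of the (min (last visit date, last dose date), 31MONYYYY, and date of death".
- **End, month missing:** the same construction with the year end, "min (last visit date, last dose date), 31DECYYYY, and date of death".
- **No imputation:** if the end year is missing or the "AE is ongoing, the end date will not be imputed".
- **Start partial, in or after the treatment-start month:** the later of the first of the recorded month and the day after a reference date, which is usually the treatment start.
- **Closing rule:** if the imputed start is later than the end, the "imputed AE start date will be set to the (imputed) AE end date". This applies to imputed starts only.

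SAP 2.8.1 defines Week 24 on-treatment AEs as "treatment-emergent AEs occurred while patients were on Epoch 3 treatment (captured using treatment start and end date". It requests on-treatment summaries of AEs, serious AEs, fatal AEs, AEs leading to discontinuation and AEs of special interest. The same section counts AEs after treatment discontinuation as treatment-emergent.

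For concomitant medications, SAP 5.1.3 adds a guard that 5.1.2 lacks: "If imputed end date is less than the start date, use the start date as the imputed end date".

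**The concern.** AEs that begin after the last dose are expected in this trial. Under protocol 5.6.2, subjects who stop study drug are not withdrawn, and AEs continue to be collected at visits or by telephone. Protocol section 6 adds a safety contact period of 30 days after the last dose.

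For such an AE, an end date capped at the last dose is impossible, because it precedes the onset. What follows depends on the start date:

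- **Start also partial:** the closing rule resolves the conflict by trusting the artificial end over the recorded start month, so an off-drug event becomes an on-drug event dated on the last dose day.
- **Start complete:** nothing resolves the conflict, and the record keeps an end before its start.

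At stake are the on-treatment summaries and any derivation that uses both dates. In a dose-finding trial that weighs weight loss against tolerability, events wrongly dated to the day of stopping are unhelpful, and diarrhea is analyzed by days with the event.

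**Working it through.** The documents give no figure to reproduce. The check applies the SAP rules to dates chosen for illustration.

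**Assumed:** first dose 8 Jan 2018, last dose 10 Mar 2018, last visit after the last dose, subject alive.
**From the SAP:** duration = end - start + 1 (2.1.1, 2.8.1.1). The last dose day counts as exposure, because exposure = last dose - first dose + 1 (2.4.1).

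**Case A: start May 2018, end May 2018, both days missing**
1. End = min(last visit, 10 Mar, 31 May) = 10 Mar.
2. This is not before the treatment start, so the reference date is 8 Jan.
3. Start = later of 1 May and 9 Jan = 1 May.
4. 1 May is after 10 Mar, so the closing rule resets the start to 10 Mar.
5. Result: 10 Mar to 10 Mar, 1 day, on-treatment. The earliest possible onset was 1 May, which is 21 + 30 + 1 = 52 days after the last dose.

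**Case B: start 5 May 2018 (complete), end May 2018**
1. End = 10 Mar, as above.
2. The start is not imputed, so the closing rule does not apply.
3. Duration = 10 Mar - 5 May + 1 = -56 + 1 = -55 days.

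**Case C: start 15 Mar 2018 (complete), end March 2018**
End = 10 Mar; duration = -5 + 1 = -4 days.

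**Unaffected:** start May with a complete end of 20 May stays 1 to 20 May, off treatment. Start May and ongoing stays 1 May with no end date.

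**Sweep.** The rules were also run with first dose 15 Nov 2017, last dose 10 Mar 2018 and last visit 17 Oct 2018. True onsets were 1 to 199 days after the last dose, with durations of 1, 5, 10 and 20 days and the end day missing: 199 × 4 = 796 combinations.

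| Start date | Date rules in SAP 5.1.2 | Cap at last visit, end not before start |
|---|---|---|
| Day missing | 796 of 796 dated on treatment | 84 of 796 dated on treatment |
| Complete | 796 of 796 end before start | 0 of 796 end before start |

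The remaining 84 are the onsets from 11 to 31 March: 21 days × 4 durations. There the first-of-month start rule alone puts the AE on treatment. With the revised cap, Case A becomes 1 to 31 May, off treatment, and Case B becomes 5 to 31 May, 27 days.

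The sweep tests the date logic and is not an incidence estimate. Some swept onsets fall after that subject's Week 24 (15 Nov 2017 + 168 days = 2 May 2018).

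**The case against.** **The effect may be small.** Protocol 7.1 requires start and end dates for AEs, and protocol 8.2 describes electronic capture with automatic discrepancy checks. The on-treatment error needs both dates partial, a known end year and an event that is not ongoing. The main Week 24 treatment-emergent tables include post-discontinuation AEs anyway, and an on-treatment set is defined only for Week 24. All of this stands and limits the point.

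**The cap has a plausible use.** For a diarrhea event that began on drug, a cap at the last dose keeps diarrhea days within the exposure offset of the negative binomial model in SAP 2.8.1.1. This also stands, and the fix has to respect it. It does not justify the rule as written, which covers all AEs, including those that began after the last dose, and leaves complete end dates uncapped.

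**Negative durations may reach few outputs.** SAP 2.8.1.1 introduces diarrhea days as on-treatment, which would exclude a complete start after the last dose. However, its per-patient sum runs over all incidences in Epoch 3, which read literally would admit one. The rule in 2.8.1 that merges AEs separated by at most 1 day also uses end dates.

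A reader might infer more than the documents support:

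- **That about 65 subjects are exposed** (15 % of 432 = 64.8). The 15 % in SAP section 3 is a sample-size allowance for losses to follow-up. It is not a rate of stopping treatment, and it is neither an estimate nor an upper bound here.
- **That SAP 5.1.1 contradicts 2.1.1 and hides early AEs.** Section 5.1.1 begins "Any partial dates will be imputed as the earlier day of" and, read literally, would move a partial first-dose date to the month end or epoch end. But 2.1.1 covers a missing date ("If the date of first administration is missing, then randomization date will be used as Day 1"), and 5.1.1 a partial one. A partial first-dose date is also unlikely, since drug is first dispensed at a dated visit. The epoch-end limit suggests a rule meant for last doses. This is loose wording.

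**Conclusion.** The point holds within a defined scope. For any AE that begins after the last dose and has a partial end date with known year, the rule assigns an end date before the true onset. If the start day is also missing and the recorded month is later than the last-dose month, the AE is moved onto treatment. If the start is complete, the duration is zero or negative. Both results follow from the text and do not depend on the calendar dates chosen. They assume that the last visit is not before the last dose and that the last dose day counts as on treatment.

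The outputs exposed are the Week 24 on-treatment summaries, possibly the diarrhea-day totals and model, and the occurrence counts based on the 1-day gap. The primary efficacy analysis is untouched, and the main treatment-emergent incidence tables are largely unchanged. The number of affected AEs cannot be derived from the documents and may be small. The correction is worth making because the rule is wrong whenever it applies to these AEs and is cheap to repair.

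**What to change.** In SAP 5.1.2:

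1. Cap partial end dates at the last contact date, or at the Week 24 cut-off for the Week 24 run, in place of the earlier of last visit and last dose. Keep the month-end, year-end and death limits.
2. Add the guard from 5.1.3: if the imputed end precedes the start, set the end to the start.
3. Do not move a start whose known month is after the last-dose month to or before the last dose.
4. State that a partial start in the last-dose month counts as on-treatment by convention, since its date cannot be resolved.

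In SAP 2.8.1.1, truncate diarrhea days at the last dose within that derivation, for complete and imputed end dates alike, so that the count matches the exposure offset. Without this step, the new cap would let diarrhea days run past the days on drug.

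As a minor clarification, state in 5.1.1 that the month-end rule applies to last-dose dates only.

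The cost is appendix wording and a small programming change, with no new data and no effect on power. A listing of AEs with a partial end date and an onset after the last dose would show at once whether any table changes. SAP 1.1 places both the Week 24 and the end of study analyses in the clinical study report, so Week 24 tables that have already been produced can be rerun for it if needed.

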5.1.3 Concomitant medication date imputation

CM date imputation need to be done twice, once for Week 24 analysis and once for the End of study analysis.

CM end date imputation

1. If 'day' is missing and 'month/year' are non-missing then impute date as the earlier of (treatment end date, and 31MONYYYY).
2. If 'day/month' are missing and 'year' is non-missing then impute date as the earlier of (treatment end date, and 31DECYYYY).
3. If imputed end date is less than the start date, use the start date as the imputed end date.

CM start date imputation

1. If 'year' is missing, the start date will be set to one day prior to treatment start date.
2. If 'year' is less than treatment start 'year', the CM started before treatment. Therefore:
 - a. If 'month' is missing, the start date will be set to 01JULYYYY.
 - b. If 'month' is non-missing, the start date will be set to 15MONYYYY.
3. If 'year' is greater than treatment start 'year', the CM started after treatment. Therefore:
 - a. If 'month' is missing, the start date will be set to 01JANYYYY.
 - b. If 'month' is non-missing, the start date will be set to 01MONYYYY.
4. If 'year' is equal to the treatment start date 'year'
 - a. If 'month' is missing or equal to the treatment start 'month', then the start date will be set to one day prior treatment start date.
 - b. If 'month' is less than the treatment start 'month', the start date will be set to 15MONYYYY.
 - c. If 'month' is greater than the treatment start 'month', the start date will be set to 01MONYYYY.

If complete (imputed) CM end date is available and the imputed CM start date is greater than the (imputed) CM end date, then imputed CM start date will be set to the (imputed) end date.

5.1.3.1 Prior therapies date imputation

See Section 5.1.3.

5.1.3.2 Post therapies date imputation

See section 5.1.3.

5.2 AEs coding/grading

AEs will be coded according to MedDRA dictionary. The MedDRA version used for reporting will be described in the footnotes. Missing severity will be assumed to be severe in the summary table.

Hypoglycemia classification is presented in Table 5-1.

Table 5-1 Hypoglycemia classification

Category	Definition	Criteria as specified in the Hypo eCRF
Severe hypoglycemia	An event, requiring assistance of another person (third party assistance) to actively administer carbohydrate, glucagon, or other corrective actions, confirmed or not by a BG measurement	An event with answer = 'YES' for any one of the two questions: 
• Was third party assistance required?• Was medical assistance received?
Other clinically significant hypoglycemia	Plasma glucose < 3.0 mmol/l (54 mg/dl)* with or without typical symptoms of hypoglycaemia, and which is handled by the subject himself/herself.	An event with answer = 'YES' to the question 'Glucose measurement taken' and the plasma glucose < 3.0 mmol/l (54 mg/dl), and answer = NO to both questions: 
• Was third party assistance required?• Was medical assistance received?

*Blood glucose values need to be converted to plasma glucose values.

A plasma glucose of 3.0 mmol/L (54 mg/dL) corresponds to a whole blood glucose of 2.7 mmol/L (48 mg/dL)
Plasma glucose = blood glucose * 1.12.

5.3 Laboratory parameters derivations

Not applicable.

5.4 Rule of exclusion criteria of analysis sets

Protocol deviations are identified prior to clinical database lock/unblinding and entered into a dedicated data panel as part of the locked database. Details are provided in the PD Specs and Edit Checks tab of LIK066B2201 Edit Check Specification document.

The protocol deviations resulting in exclusion of subjects from an analysis population are outlined in Table 5-1 below.

Table 5-2 Protocol deviations that cause subjects to be excluded

Deviation ID	Description of Deviation	Exclusion in Analyses
INCL01	Informed consent not obtained	Excluded from SCR, RUN, RAN, FAS, SAF, and PPS
TRT19	Subject withdrew consent and not discontinued from the study	Data collected after withdrawal of IC, excluded from FAS and SAF
TRT34	Patients mis-randomized in IRT	Excluded from FAS and PPS
INCL03	BMI not within range or BMI missing	Excluded from PPS
EXCL04	Subject taking prohibited medication	Excluded from PPS
EXCL05	Patient with a history of malignancy	Excluded from PPS
EXCL06	Pregnant patient	Excluded from PPS
EXCL08	Use of active weight-loss medications	Excluded from PPS
EXCL09	Bariatric surgery	Excluded from PPS
EXCL10b	Not compliant with lifestyle intervention	Excluded from PPS
EXCL19	Substances or alcohol abuse	Excluded from PPS
TRT06	Study treatment adjusted	Excluded from PPS
TRT11	Study treatment unmasked and subject not discontinued from the study	Excluded from PPS
TRT15	Use of prohibited medication and not discontinued from the study	Excluded from PPS
TRT22	Use of another investigational drug while on study	Excluded from PPS
TRT35	Study medication taken after the morning or evening meal	Excluded from PPS
TRT28	Misdispensed medication and taken by patient	Excluded from PPS

[figure not shown]
Table 5-3 Subject Classification

Analysis Set	PD ID that cause subjects to be excluded	Non-PD criteria that cause subjects to be excluded
SCR	INCL01	Not having screening epoch disposition page

Analysis Set	PD ID that cause subjects to be excluded	Non-PD criteria that cause subjects to be excluded
RUN	INCL01	Not in ENR; Not having run-in epoch disposition page
RAN	INCL01	Not randomized
FAS	INCL01, TRT19, TRT34	Not in RAN;
PPS	INCL01, INCL03, EXCL04, EXCL05, EXCL06, EXCL08, EXCL09, EXCL10b, EXCL19, TRT06, TRT11, TRT15, TRT22, TRT35, TRT 28, and TRT34	Overall exposure on DB medication < 22 weeks unless premature discontinuation due to adverse events
SAF	INCL01, TRT19	No double-blind study drug taken

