2.2 Analysis sets

Screened set (SCR): the SCR consists of all subjects who signed the ICF.

Randomized set (RAN): All subjects who have received a randomization number, regardless of receiving trial medication.

Run-in set (RUN): All subjects who enter the run-in epoch.

Full analysis set (FAS): the FAS comprises all subjects to whom study treatment has been assigned, except those who are not qualified for randomization but were inadvertently randomized into the study and did not take any study drug. Following the intent-to-treat principle, subjects will be analyzed according to the treatment assigned to at randomization.

Safety set (SAF): the SAF includes all subjects who received at least one dose of study medication. Subjects will be analyzed according to treatment received. Note that the safety set allows the inclusion of non-randomized subjects who received the study drug in error.

Per-protocol set (PPS): the PPS is a subset of the FAS. It consists of all randomized subjects in the FAS who have been exposed to study medication for at least 22 weeks and have no major protocol deviations (PDs) affecting the primary endpoint analysis.

Randomized set – Epoch 4 (RAN-Epoch 4): all randomized subjects who have been assigned a treatment in Epoch 4.

Full analysis set – Epoch 4 (FAS-Epoch 4): all RAN-Epoch 4 subjects, excluding those who did not take any Epoch 4 study medication.

Safety set – Epoch 4 (SAF-Epoch 4): all SAF subjects who received at least one dose of Epoch 4 study medication.

Protocol deviations will be pre-specified prior to un-blinding treatment codes for analyses. See Appendix Table 5-2 and Table 5-3 for list of protocol deviations and criteria that lead to exclusion from analysis sets, and related rules of exclusion criteria of analysis sets.

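### SAP Tables 5-2 and 5-3 exclude mis-randomized subjects (TRT34) from the FAS more widely than the FAS definition allows, and Table 5-3 contradicts Table 5-2 on consent withdrawal (TRT19)

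*SAP*

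**What the plan says.** SAP 2.2 puts in the FAS every subject who was assigned study treatment, "except those who are not qualified for randomization but were inadvertently randomized into the study and did not take any study drug". Protocol 9.1 has the same exception. Both then state: "Following the intent-to-treat principle, subjects will be analyzed according to the treatment assigned to at randomization". For safety, SAP 2.2 says that "the SAF includes all subjects who received at least one dose of study medication". The PPS is defined as a subset of the FAS. SAP 2.2 sends the reader to Tables 5-2 and 5-3 for the exclusions, so those tables are the working rules.

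Table 5-2 (SAP 5.4) is titled "Protocol deviations that cause subjects to be excluded". Two of its rows matter here:

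- TRT34, "Patients mis-randomized in IRT": the subject is excluded from the FAS and the PPS.
- TRT19, "Subject withdrew consent and not discontinued from the study": the consequence is "Data collected after withdrawal of IC, excluded from FAS and SAF".

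Table 5-3 then gives, for each analysis set, the deviation codes that exclude a subject. The FAS row reads "INCL01, TRT19, TRT34". The SAF row has INCL01 and TRT19. The PPS row includes INCL01 and TRT34 but not TRT19. Besides deviation codes, the FAS row names only absence from the randomized set, the SAF row only that no double-blind drug was taken, and the PPS row only an exposure criterion.

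**The concern.** The FAS carries the primary dose-response analysis (SAP 2.5.1) and the SAF carries the safety analyses (SAP 2.8). A set rule broader than its definition takes randomized subjects out after randomization, which the intent-to-treat statement is there to prevent. For TRT19, a program written from Table 5-3 would also take a subject's adverse events and laboratory values from before consent withdrawal out of the SAF summaries.

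The risk of divergent implementation is practical. SAP 5.6.1 assigns the Week 24 and end-of-study analyses to two separate groups. Two groups working from tables that disagree could derive different sets. SAP Section 4, which records departures from the protocol analyses, mentions only the hsCRP endpoint, so a narrower FAS is not declared as an intended change.

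**Working it through.** There is no figure in the plan to reproduce; this is a check of texts against one another. INCL01 (no informed consent) is left aside.

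Each type of subject was followed through the definitions and the two tables:

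| Subject | SAP 2.2 and protocol 9.1 | Table 5-2 | Table 5-3 |
|---|---|---|---|
| Mis-randomized, unqualified, no drug taken | Out of FAS, out of SAF | Out of FAS | Out of FAS, out of SAF |
| Mis-randomized, took drug | In FAS, in SAF | Out of FAS | Out of FAS, in SAF |
| Mis-randomized, qualified, no drug taken | In FAS, out of SAF | Out of FAS | Out of FAS, out of SAF |
| TRT19, took drug before withdrawing consent | In FAS, in SAF | In both, later data removed | Out of FAS, out of SAF |

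**TRT34.** The FAS exception has three conditions that must hold together. The tables agree with the definitions only in the first line. In the second and third lines at least one condition fails, so the definition keeps the subject and both tables remove the subject. The second line is the one that matters most: the subject was treated, counts for safety, and is absent from the primary analysis.

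**TRT19.** The Table 5-2 cell removes data, not the subject. Protocol 5.6.3 points the same way: after withdrawal no further assessments are made and what would have been collected later counts as missing. Under that rule the subject stays in the FAS with the weights recorded before withdrawal, and a missing Week 24 value is handled by the multiple imputation of SAP 2.5.3. Under Table 5-3 the subject contributes nothing to either set. Only the Table 5-3 rule conflicts with the FAS and SAF definitions.

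**PPS nesting.** Take a TRT19 subject with at least 22 weeks of exposure and no other listed deviation. The FAS row of Table 5-3 removes this subject and the PPS row does not, so the subject is in the PPS but not in the FAS. This follows only if TRT19 is read as a whole-subject exclusion. Apart from that, the TRT19 row of Table 5-2 names the FAS and SAF but not the PPS, so the data cut is not stated for the PPS sensitivity analysis (SAP 2.5.4).

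**Scale.** Neither document says how many subjects carry either code. Per subject removed:

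- planned arm of 36: 1/36 = 2.8%
- planned arm of 72: 1/72 = 1.4%
- all 432 planned subjects: 1/432 = 0.23%

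These describe one hypothetical subject. They do not estimate an effect.

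**The case against.** The strongest reply on TRT34 is that the code may be no more than the programming label for the FAS exception. No other entry in the FAS row of Table 5-3 could carry that exception. Its absence from the SAF row fits this, because untreated subjects leave the SAF anyway. Neither document defines mis-randomization in the IRT, and SAP 5.4 refers to an Edit Check Specification that is not available here. This may well be the intention. But the no-drug condition is written in neither table, and the flag for misrandomized subjects in the SAP 2.3.2 disposition listing, which shows the date of last dose, is not limited to untreated subjects.

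On TRT19, a reader might infer from the title of Table 5-2 that both tables drop whole subjects. The documents do not support that: the TRT19 row itself is specific to data after withdrawal. The PPS entries also favor the data cut, since INCL01 and TRT34, the two whole-subject FAS exclusions, are repeated for the PPS in both tables and TRT19 is not. So the data cut is probably what was meant. The objection stands as to intent, but Table 5-3 still states a different rule.

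Safeguards limit the harm. Deviations are identified before database lock and unblinding (SAP 5.4). Exclusions are listed with reasons (SAP 2.3.2). All adverse events in the database are listed by randomized arm (SAP 2.8.1), so under Table 5-3 events before withdrawal would leave the SAF summaries but not the listings. None of this settles which rule applies.

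**Conclusion.** The point holds as an inconsistency in the written set rules. The TRT34 rule in both tables is broader than the FAS definition and, as written, removes treated randomized subjects from the primary analysis. On TRT19, Table 5-3 contradicts Table 5-2 and the FAS and SAF definitions. The PPS nesting fault depends on reading Table 5-3 literally.

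A reader might go further and infer that treated subjects will in fact be lost or that the primary result is biased. The documents do not show this. There are no counts, the unseen specification may narrow TRT34, and TRT19 requires both a withdrawal of consent and a failure to discontinue the subject. The effect cannot be quantified and is probably small. The conclusion rests on the SAP text alone, which should define its primary analysis set without help from another document.

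**What to change.** - TRT34: in Tables 5-2 and 5-3, limit the FAS exclusion to subjects who were not qualified, were randomized in error and took no study drug. The PPS exclusion can stay as it is.
- TRT19: in Table 5-3, take the code out of the subject-level column for the FAS and SAF. Apply it as the cut at the date of consent withdrawal that Table 5-2 already states, and say that the cut also covers PPS analyses.
- PPS: add *Not in FAS* to the criteria in the PPS row of Table 5-3, so that the derivation enforces the subset relation in SAP 2.2.

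If a narrower FAS was intended, it should instead be declared and justified in SAP Section 4. The cost is table wording and set-derivation code; no new data, visits or analyses are needed.
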